19.4 DISCRETE EVENT SIMULATION MODEL TO MEASURE COST-EFFECTIVENESS AND COST-BENEFIT

A discrete event simulation model (see figure this page) is used to measure the costs (e.g., clinical human resources, medical supplies, drugs, diagnostics, investigations and CelluTome) and consequences (e.g., healing, clinical infection, hospitalization and death) over the course of the study time period from the perspective of the hospital/outpatient, payer and patient. The model will contain health states (e.g., healed ulcer, infected ulcer, severely infected ulcer, hospitalization (e.g., cellulitis, amputation), uncomplicated ulcer and death). The patient and respective ulcer will travel over time in the model for three years accumulating costs and consequences. Cost analysis for differing perspectives and time-horizons are completed using the advantages of the model framework.

In particular, average quality of life utility score values will be assigned to

CELLUTOME™ IN VENOUS LEG

each health state from the use of Wound-Trade©, time trade-off assessment (Appendix 19.2) matched to the health states in a separate matching analysis between scores and health state of the ulcer/patient measured in the case report form. As the patient/ulcer traverses through the model over time weekly assigned utility values in each health state will be compiled and totaled for each patient and respective group at years end. This will facilitate the determination of cost per quality adjusted life year comparison between groups.

A cost-benefit (return-on-investment) measurement will also be completed from the hospital/outpatient perspective to show value to the institution. Average direct medical costs attributed to resource utilization, medical supplies, drugs, diagnostics and CelluTome™ will be estimated during the trial for each group. Financial benefits include averted costs of complications from rapid healing that may be consequential to the hospital/outpatient clinic.

Cost-effectiveness is used to demonstrate the value of CelluTome™ for rapid healing, reduced complications and therefore reduced financial impact for the payer.

Return-on Investment Metrics:

Metric	Definition	Formula
Costs	Total amount of money spent on new improvement process	$= \sum_{i=1}^n \text{Cost}_i$
Benefits	Total amount of money gained from a new and improved process	$= \sum_{i=1}^n \text{Benefit}_i$
Net present value	Discounted benefits based on inflation	$= \frac{\text{Benefits}}{(1 + \text{Inflation_Rate})^{\text{Years}}}$

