institutions participating in the study. For resource consumption outside of the wound clinic national hourly wage rates will be determined for home care visits, nursing home staff, family caregiver etc. as detected in modified activity-based costing data collection forms. All direct medical costs from the hospital/outpatient sector will be compiled for each cohort and compared between groups as the patients flow through the study/system. This allows a pragmatic view of costs and cost savings from the hospital/outpatient perspective in relation to their charges and reimbursement.

Payer Perspective: Reimbursement from Medicare, Medicaid and Private payers during the course of the study for each group are compiled from each institution participating in the study. Average reimbursement for each product/procedure/stay for each cohort and patient will be determined across the institutions. This information will come from data sources within each institution as compiled by an internal research assistant. Cost effectiveness analysis from the payer perspective is expected to show reduced reimbursement costs for CelluTome group in respect to expedited healing and reduction in complications.

[figure not shown]
Patient Perspective: Patient costs will be determined from the patient or proxy related to the direct care (medicine, hospital, therapy etc.) that are out-of-pocket, indirect work loss, worker replacement, and reduced productivity from the ulcer.

A comparative cost-benefit, cost-utility and cost-effectiveness analysis will be derived from a discrete-event simulation model with a time-frame conducive to each perspective above (Appendix 19.4). For the hospital/outpatient clinic a return-on-investment (cost-benefit) is determined over 6 to 12 treatment weeks which is standard length-of-time patient is engaged with that sector. From a payer perspective, the model will highlight costs from 1 to 3 years as VLU patients that do not heal within 6 months continue with treatment expenses. Fortunately, patients that do not heal within 6 months are few (~10 percent) but still costly. Reduction in patient out-of-pocket expenses will be compared over the entire span of the model (3 years).

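### The net present value in Appendix 19.4 has no cost term, so it measures gross benefit and cannot show a loss

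*Combined protocol and SAP*

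**What the plan says.** The Synopsis lists cost-benefit at 12 weeks among the study endpoints. Section 3 lists cost-benefit as a secondary outcome and refers to Appendix 19.4.

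Appendix 19.4 states the purpose: "A cost-benefit (return-on-investment) measurement will also be completed from the hospital/outpatient perspective to show value to the institution". It describes the two sides of the account:

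- On costs: "Average direct medical costs attributed to resource utilization, medical supplies, drugs, diagnostics and CelluTome™ will be estimated during the trial for each group".
- On benefits: "Financial benefits include averted costs of complications from rapid healing that may be consequential to the hospital/outpatient clinic".

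The table of return-on-investment metrics then has three rows:

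- Costs: "Total amount of money spent on new improvement process", the sum of Cost_i.
- Benefits: "Total amount of money gained from a new and improved process", the sum of Benefit_i.
- Net present value: "Discounted benefits based on inflation", with the formula Benefits / (1 + Inflation_Rate)^Years.

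Appendix 19.3 sets the horizon for the hospital or outpatient clinic: "a return-on-investment (cost-benefit) is determined over 6 to 12 treatment weeks".

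**The concern.** A net present value sets discounted benefits against discounted costs. The row with that name contains benefits only, and its verbal definition and its formula agree in leaving costs out. Benefits cannot be read as already net, because money spent has its own row and the text describes benefits as averted complication costs, which is a gross saving.

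No other part of the plan supplies the missing step. None of hypotheses H1 to H8 in Section 9.2 concerns cost-benefit, and Section 9.7 gives no cost-benefit method and lists no cost variable. The one formula that takes a cost difference is the cost-per-QALY ratio in Appendix 19.2, which belongs to the cost-utility analysis.

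If the formula is followed as printed, a gross benefit will be reported under a label that readers take to mean a net one. Where grafting costs the institution more than it saves, the reported figure will have the wrong sign.

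**Working it through.** The plan states no cost, benefit, inflation rate or net present value, so there is no figure of its own to reproduce. The check is of the formula.

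**Sign of the printed metric.** Write B for total benefits, C for total costs, r for the rate and Y for years. The printed metric is B / (1 + r)^Y. The denominator is positive for any r above -100%, so the metric takes the sign of B. C does not appear, so no change in costs can alter it.

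**Illustration.** Assumed, not from the documents: B = $1,000, C = $1,500, r = 3%, both amounts falling at 12 weeks, so Y = 12/52 = 0.231.

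- Discount factor: 1 / 1.03^(12/52) = 0.9932.
- Printed formula: 1,000 × 0.9932 = +$993.20.
- Net of costs: (1,000 − 1,500) × 0.9932 = −$496.60.

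The timing of costs makes little difference. If all costs fell at time zero, the net value would be 993.20 − 1,500 = −$506.80.

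**Other assumed benefits**, with C = 1,000, r = 3% and 12 weeks:

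| Benefits | Printed formula | Net, both at 12 weeks | Net, costs at time zero |
|---|---|---|---|
| 1 | +0.99 | −992.21 | −999.01 |
| 500 | +496.60 | −496.60 | −503.40 |
| 1,000 | +993.20 | 0 | −6.80 |
| 1,500 | +1,489.80 | +496.60 | +489.80 |

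The third column is (B − C) × 0.9932; the fourth is B × 0.9932 − C. When benefits and costs share a date, the printed sign is wrong exactly when 0 < B < C. When costs come earlier, it is also wrong for benefits equal to costs or very slightly above them.

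**How much the rate and exponent matter.** At 12 weeks and r = 7%, 1,000 becomes 984.51, a reduction of 15.49 / 1,000 = 1.5%. At 6 weeks it becomes 992.22, a reduction of 0.8%. Over the 6 to 12 week horizon and rates of 0 to 7%, discounting therefore changes the figure by at most about 1.5%. The missing cost term is what matters.

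**The case against.** A reader might infer that the whole cost-benefit result is bound to be positive. The documents do not support that. Costs are a reported metric in the same table, Appendix 19.4 has direct medical costs estimated for each group, and the cost analysis in Appendix 19.3 compiles direct hospital and outpatient costs by cohort and compares them between groups. Nor does the plan say that net present value alone decides the cost-benefit outcome. A careful reader of the report could put the totals side by side and see a loss. This objection stands, and it confines the point to the net present value row. It does not rescue that row, because no formula or rule tells anyone to make the subtraction.

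A reader might also make much of inflation standing in for a discount rate, and of a single power of years applied to an undated total. Both are loose, but over the stated hospital horizon their effect is at most about 1.5%. They would matter more over three years (at 7%, 1,000 becomes 816.30), but Appendix 19.3 ties the return-on-investment measure to 6 to 12 weeks.

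It would also be wrong to infer that the device, labour or supplies have been left out of the costing. Appendices 19.3 and 19.4 already list them; they simply do not reach this formula.

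Finally, the table was read from a PDF, and a separate return-on-investment row may have been lost. That cannot be excluded. The net present value row itself is complete in both definition and formula, so the point about it does not depend on what else the table held.

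**Conclusion.** The net present value row is wrong as written. It gives the present value of gross benefits, it is positive whenever benefits are positive, and it cannot register a loss. This follows from the algebra and needs no assumed figures. The dollar amounts are illustrative only: under the stated assumptions the printed value is about +$993 against a net value of about −$497.

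The finding covers that row, not every cost comparison the plan will report. It concerns a secondary economic outcome that no stated hypothesis tests, and it leaves the primary endpoint, alpha, power and sample size untouched. It should be corrected before the economic analysis is run.

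**What to change.** Replace the formula with NPV = Σ_t (Benefit_t − Cost_t) / (1 + r)^t, where benefits and costs are differences between the groups, t is time in years, and r is a rate stated in advance. Take Cost_t from the costs already to be collected under Appendix 19.3. Say that a complication cost counted as averted in Benefit_t is not counted again in Cost_t.

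If the source table has no return-on-investment row, add ROI = (Benefits − Costs) / Costs, since the section promises that measure. With the assumed figures above it is (1,000 − 1,500) / 1,500 = −33%. The choice of rate needs only a sentence, given its small effect over 6 to 12 weeks.

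The change is one or two lines in an appendix and needs no new data. Its downside for the sponsor is that the reported economic result may be less favourable than under the printed formula.

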19.5 QUALITY OF LIFE QUESTIONNAIRE (w-QOL)

Quality of life with chronic wounds – "W-QoL" questionnaire

With the following questions, we aim to find out how your chronic wound(s) affect(s) your quality of life.

In every line, please tick what has applied to you in the last 7 days.

	In the last seven days...	not at all	a little	moderately	quite a lot	very much
1	...my wound hurt					
2	...my wound had a bad smell					
3	...there was a disturbing discharge from the wound					
4	...the wound has affected my sleep					
5	...the treatment of the wound has been a burden					
6	...the wound has made me unhappy					
7	...I have felt frustrated because the wound is taking so long to heal					
8	...I have worried about my wound					
9	...I have been afraid of the wound getting worse or of new wounds appearing					
10	...I have been afraid of knocking the wound					
11	...I have had trouble moving about because of the wound					
12	...climbing stairs has been difficult because of the wound					
13	...I have had trouble with day-to-day activities because of the wound					
14	...the wound has limited my leisure activities					
15	...the wound has forced me to limit my activities with others					
16	...I have felt dependent on help from others because of the wound					
17	...the wound has been a financial burden to me					

"W-QoL" questionnaire. German Center for Health Services Research in Dermatology (CVderm), University Medical Center Hamburg
Items adapted from Freiburg Quality of Life Assessment (FLQA-w), Würzburg Wund Score (WWS), Cardiff Wound Impact Schedule (CWIS)

19.6 PBI-P – PATIENT BENEFIT INDEX, WOUND VERSION

At the beginning of treatment for each group a patient benefit index questionnaire is given to the patient for completion. It is intended to give the patient a chance to give their goals of treatment:

PBI-P – Patient Benefit Index, wound version

Importance of Treatment Goals

With the help of the following questions, we'd like to know how important the below mentioned goals are to you personally in the **current treatment**.

For each of the following statements, please mark **how important** this treatment goal is to you. If a statement does not apply to you, e.g. because you do not have pain, please mark "*does not apply to me*".

As a result of therapy, how important is it for you to ...		not at all	somewhat	moderately	quite	very	does not apply to me
1	...be free of pain						
2	...have no discharge from the lesion						
3	...not have an unpleasant smell from the lesion						
4	...be healed from the lesion(s)						
5	...be able to sleep better						
6	...feel less depressed						
7	...experience a greater enjoyment of life						
8	...have no fear that the disease will become worse						
9	...be able to lead a normal everyday life						
10	...be more productive in everyday life						
11	...be less of a burden to relatives and friends						
12	...be able to engage in normal leisure activities						
13	...be able to lead a normal working life						
14	...be able to have more contact with other people						
15	...be comfortable showing yourself more						
16	...be less burdened in your partnership						
17	...be less dependent on doctor and clinic visits						
18	...need less time for daily treatment						
19	...have fewer out-of-pocket treatment expenses						
20	...have fewer side effects						
21	...find a clear diagnosis and therapy						
22	...have confidence in the therapy						

Please check once more if you have exactly marked each statement with an 'x'.

Our sincerest thanks for your cooperation!

PBI-Patient Benefit Index (index of benefits and needs in therapy), Augustin 2006

At the end of treatment, the patient will complete the form below indicating if the respective treatment met their goals:

PBI-P – Patient Benefit Index, wound version

Treatment benefits

At the start of the treatment, you indicated in a questionnaire how important various goals were in the treatment of your skin disease.

Please mark each of the following statements according to the extent that these treatment goals **were achieved**, thereby indicating if the treatment has benefitted you. If a statement did not apply to you, e.g. because you had no pain, please mark "did not apply to me".

The current treatment has helped me to...		not at all	somewhat	moderately	quite	very	did not apply to me
1	...be free of pain						
2	...have no discharge from the lesion						
3	...not have an unpleasant smell from the lesion						
4	...be healed from the lesion(s)						
5	...be able to sleep better						
6	...feel less depressed						
7	...experience a greater enjoyment of life						
8	...have no fear that the disease will become worse						
9	...be able to lead a normal everyday life						
10	...be more productive in everyday life						
11	...be less of a burden to relatives and friends						
12	...be able to engage in normal leisure activities						
13	...be able to lead a normal working life						
14	...be able to have more contact with other people						
15	...be comfortable showing yourself more						
16	...be less burdened in your my partnership						
17	...be less dependent on doctor and clinic visits						
18	...need less time for daily treatment						
19	...have fewer out-of-pocket treatment expenses						
20	...have fewer side effects						
21	...find a clear diagnosis and therapy						
22	...have confidence in the therapy						

Please check once more if you have exactly marked each statement with an 'x'.

Our sincerest thanks for your cooperation!

PBI-Patient Benefit Index (index of benefits and needs in therapy), Augustin 2006

19.7 SWAB COLLECTION PROCEDURE

1. Ensure that complete haemostasis has been achieved before obtaining the specimen.
2. Moisten wound area to be swabbed with saline. Care should be taken not to flood the wound with excessive saline.
3. Use the swabs provided by the Sponsor(s).
4. Avoid swabbing areas that contain blood, necrotic material or thick slough.
5. Press the head of the swab flat against the base of the wound and gently rotate it back and forth several times while applying pressure. Continue rotating the swab head until it is fully coated with wound fluid. The head of the swab should turn a tan color.
6. Collect additional swabs using the same procedure described in step 5 above. Apply additional saline drops to remoisten the wound between swabs.
7. Label the swabs with Subject ID#, date, and study visit number.

19.8 ANTIMICROBIAL DRESSING

In order to reduce the risk of infection, any of the following dressing may be used during the 2 week screening period and during TV4, TV8, and TV10 (for patients crossing over):

Prisma
Silver Alginate
Silver Hydrogel
Honey
Hydrofera blue

19.9 APPLICATION OF PRISMA™

1. Clean wound with saline; dry peri-wound skin
2. Cut Prisma™ to cover the wound bed
3. Apply Prisma™ directly on the wound if it is moist. Normal saline may be used for dry wounds before Prisma™ is applied.
4. Apply appropriate cover dressing to maintain a moisture balanced wound environment. Prisma™ will be absorbed over 3 days. Prisma™ may need replacing more frequently if wound is exudating heavily.

19.10 EPIDERMAL HARVESTING PROCEDURE

- Select donor site (inner thigh).
- Using clippers to remove any hair from the skin. (Do not use a razor to shave the patient)
- Prep the site with isopropyl alcohol.
- Anesthesia is not required.
- Apply the harvester and affix in place using the Velcro strap.

[figure not shown]

- Attach the vacuum hood. Press on the opposite sides of the hood until you here a click. This ensures that you have a seal.

- Turn the machine on. The vacuum head will apply 200 mmHg negative pressure and heat the skin to 40 C. The patient may experience a warm feeling.
- The epidermal microdomes are ready for harvesting when the epidermis has formed blisters as shown.

[figure not shown]
CELLUTOME™ IN VENOUS LEG

- Turn off the power.
- Remove the vacuum hood.
- Place the foam dressing provided in the harvester.

[figure not shown]

- Pull the blue handle back until you hear a “click.”
- Place the foam dressing provided in the harvester. Activate the blades cutting the epidermal microdomes by advancing the blue handle back onto the harvester.

CELLUTOME™ IN VENOUS LEG

- Examine the foam and record the percentage of microdomes harvested.

- Transfer the foam to the wound and secure using the 3M Coban-2 compression wrap.

- Cover the donor site with Tegaderm® provided.
